8.4.4.2 Janssen Special Reporting Situations

Safety events of interest for a Janssen medicinal product that require expediting reporting and/or safety evaluation include, but are not limited to:

- Drug exposure during pregnancy (maternal and paternal)
- Overdose of a Janssen medicinal product
- Exposure to a Janssen medicinal product from breastfeeding
- Suspected abuse/misuse of a Janssen medicinal product
- Inadvertent or accidental exposure to a Janssen medicinal product
- Any failure of expected pharmacological action (i.e., lack of effect) of a Janssen medicinal product
- Medication error involving a Janssen medicinal product (with or without patient exposure to the Janssen medicinal product, e.g., name confusion)
- Suspected transmission of any infectious agent via administration of a medicinal product
- Unexpected therapeutic or clinical benefit from use of a Janssen medicinal product

These safety events may not meet the definition of an adverse event; however, from Janssen Scientific Affairs, LLC perspective, they are treated in the same manner as adverse events. Special situations should be recorded on the Adverse Event page of the CRF.

8.5 STUDY HALTING RULES

Safety assessments will consist of monitoring and recording all adverse events and serious adverse events, the regular monitoring of hematology and blood chemistry parameters and regular physical examinations. Adverse events will be evaluated continuously throughout the study. Safety and tolerability will be assessed according to the NIH/NCI Common Terminology Criteria for Adverse Events version 5.0 (CTCAE v5.0) that is available at: <http://evs.nci.nih.gov/ftp1/CTCAE/About.html> The Protocol Monitoring Committee (PMC) at Moffitt monitors its assigned ongoing research protocols for: adverse event reporting, data and safety monitoring, and internal audit findings. The PMC, upon review of any agenda item, may approve the study for continuation, require revisions, suspend or close a protocol.

Investigators of studies which are designated to be reviewed by the PMC for data and safety monitoring, shall provide a statistical report of the study's progress and summary of adverse events and deviations based on the phase of the study and the associated risk of the study or more often if applicable. The PI will be notified for recommendations or notifications after the PMC review in regards of continuation or stopping the clinical trial

8.6 SAFETY OVERSIGHT

Serious Adverse Events: Serious Adverse Events (SAEs) from this protocol will be reported concurrently to the IRB and the study sponsor within 24 hours of staff awareness of the event. The Protocol Monitoring Committee (PMC) will review these SAEs in accordance with their policy. The data and safety plan will define dose limiting toxicities, rules for escalation of dose, and criteria for stopping the trial according to rules set forth by this protocol. This trial will be continuously monitored by the PI and the research team. A final safety and monitoring report will be submitted to the PMC. This protocol will be subject to periodic internal audits based on risk or as recommended by the PMC.

9 CLINICAL MONITORING

Data will be captured in OnCore, Moffitt's electronic Clinical Trials Database. For each participant enrolled, the electronic CRF must be completed by the assigned data manager or other authorized study staff. Any paper forms should be typed or filled out indelible ink and must be legible. Errors should be crossed out but not obliterated, the correction inserted, and the change initialed and dated by the investigator or his/her authorized delegate. This also applies to records for those patients who fail to complete the study. If a patient stops dosing or terminates from the study, the dates and reasons must be noted on the CRF. If a patient terminates from the study because of a DLT, thorough efforts should be made to clearly document the outcome. Regulatory documents and case reports forms will be monitored internally according to the Moffitt Cancer Center monitoring policies. Monitoring will be performed regularly by the MCC Clinical Monitoring Core for accuracy, completeness, and source verification on data entry, validation of appropriate consent process, reporting on SAEs, and adherence of the protocol, GCP guidelines and applicable regulatory requirements.

10 STATISTICAL CONSIDERATIONS

10.1 STATISTICAL AND ANALYTICAL PLANS

Enrolled patients will be evaluable for response assessment if receiving at least 4 weeks into ibrutinib therapy and at least 2 cycles of pembrolizumab. It will be used for efficacy and safety analysis. The primary endpoint of this trial is the complete response (CR) with the hypothesis of obtaining CR in 30% of patients and the secondary end point is the overall response rate (ORR, the immune response to the vaccine measured as T cell subset alterations, B-cell immune response potency to the vaccine and the cytokine patterns in treated patients. Exact binomial 95% confidence intervals for the true ORR will be calculated.

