3 OBJECTIVES AND PURPOSE

Objective:

This is designed as a phase II study intended to evaluate the impact of sequential overlapping treatment with PD-1 monoclonal antibody (mAb), pembrolizumab/MK-1375, followed by ibrutinib on endogenous immune function in previously untreated, high-risk CLL patients (defined as presence of del17p or TP53, del11q or ATM mutation, unmutated IGVH or mutated IGVH with 3.21 phenotype) with absolute lymphocyte count >20,000 but without meeting iwCLL criteria to start therapy.

Primary Objectives:

1. Assessment of the complete response (CR) of CLL to therapeutic intervention (defined per current iWCLL 2008 response criteria)
2. Time to response of CLL to therapeutic intervention (defined as time to achievement of response according to iWCLL 2008 criteria).

Secondary Objectives

1. Assessment of the overall response rate (ORR) [CR + PR] per iWCLL 2008 response criteria
2. Restoration of immune response as measured by:
 - a. Decreased markers of T-cell exhaustion
 - b. Increased of quantitative immunoglobulin levels and subtype
2. Safety and toxicity of the combination
3. Progression free survival (PFS)
4. 3. Incidence of Richter's transformation (defined as transformation of CLL into an aggressive lymphoid/histiocytic histology including well defined World Health Organization 2008 subtypes). Richter's transformation should be biopsy proven

Exploratory Objectives:

1. Alterations in T lymphocyte function, including changes in:
 - a. TH1:TH2 polarization, and TReg:TH17 distributions
 - b. Markers of T cell exhaustion and/or inhibition
 - c. Alterations in distribution of naïve vs. memory
 - d. Cellular activation and cell-mediated cytotoxic capacity
2. Alterations in B lymphocyte function, including changes in:
 - a. Serum anti-pneumococcal antibody titers in response to Prevnar vaccination
 - b. Quantitative serum immunoglobulin levels and subtyping
 - c. Fc-receptor (FcR) expression patterns
3. Alterations in global systemic cytokine patterns: Includes IFN- γ , TNF- α , IL-2, IL-4, IL-10, IL-6, IL-17A, allowing discrimination between TH1, TH2, and TH17 profiles (described in Section 4.2.2.2)

Hypothesis for Primary and Secondary Objectives:

The therapeutic combination of PD1:PDL1 blockade (PDB) and ibrutinib can improve the severe immune dysfunction classically associated with CLL, thereby improving disease-related morbidity and mortality in high-risk, previously untreated patients.

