5.4.2 HANDLING OF PARTICIPANT WITHDRAWALS OR TERMINATION

Every effort will be made to maintain contact with a subject who withdraws early. If the subject remains at MCC for further care, clinic visits may be tracked and the condition of the subject followed. If the subject is not continuing care at MCC, contact information will be updated at the end of treatment visit, including accurate phone numbers, and email address. The importance of the follow-up period for AEs and SAEs will be stressed to the subject.

Replacement of participants who screen fail or drop out prior to completing 9 weeks of treatment are permitted to be replaced in order to meet the accrual goal of this study.

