10.2 DESCRIPTION OF STATISTICAL METHODS

10.2.1 ANALYSIS OF THE PRIMARY EFFICACY ENDPOINT(S)

The Simon's minmax two-stage design will be used to test the null hypothesis that complete response (CR) \leq 10% versus the alternative that CR \geq 30% with 90% power and a type I error rate of 10%. This will result in an expected sample size of 20.37 and a probability of early termination of 0.52. After testing the drug combination on 16 patients in the first stage, the trial will be terminated if 1 or fewer respond. If the trial goes on to the second stage, a total of 25 patients will be studied. If the total number responding is less than or equal to 4, the drug combination will be rejected. Statistical analyses will be descriptive in nature. Patients' demographics, AEs and serious AEs, disease status, and CR will be summarized by descriptive statistics.

Clinical response rates will be calculated with 95% CIs.

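### The CR denominator leaves out, and the plan allows replacing, treated patients who stop early; this biases the CR rate upward and can take the Simon type I error above 10% if the null applies to all treated patients

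*Combined protocol and SAP*

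**What the plan says.** Section 3 gives the first primary objective as "Assessment of the complete response (CR) of CLL to therapeutic intervention". Section 4.1 describes that intervention as pembrolizumab from the start, with daily ibrutinib added at week 6.

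Section 10.1 defines the response set: "Enrolled patients will be evaluable for response assessment if receiving at least 4 weeks into ibrutinib therapy and at least 2 cycles of pembrolizumab". It adds that this set serves both efficacy and safety.

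Section 5.4.2 covers screen failures and early drop-outs together. Those who "drop out prior to completing 9 weeks of treatment are permitted to be replaced in order to meet the accrual goal of this study". It does not separate dosed from undosed patients and excepts no reason for stopping. The discontinuation reasons in Section 5.4.1 include unacceptable adverse events and intercurrent illness.

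Section 6.1.9 has another evaluability rule: 9 weeks or three pembrolizumab infusions, with no ibrutinib requirement.

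Section 10.2.1 sets a Simon minimax design "with 90% power and a type I error rate of 10" percent, for a CR rate of 10% against 30%. The stage 1 rule is: "After testing the drug combination on 16 patients in the first stage, the trial will be terminated if 1 or fewer respond". Then: "If the trial goes on to the second stage, a total of 25 patients will be studied", and the combination is rejected at 4 or fewer CRs. The section does not say whether the 16, the 25 and the 10% null refer to treated or to evaluable patients. Neither Section 5.4.2 nor Section 10 states an all-treated CR analysis or a rule counting missing responses as non-CR.

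**The concern.** The objective concerns the regimen, which begins with the first pembrolizumab infusion. The response set begins about ten weeks later. The first scheduled response assessment is at week 12 (Section 7.1.15), and the post-treatment marrow comes 28 to 35 days after week 51 (Section 7.1.16). After early discontinuation, both CT and marrow are at the investigator's discretion. A patient who stops all treatment before week 10 therefore has almost no route to a documented CR. Removing such patients takes out non-CRs and essentially nothing else, so the error runs in one direction.

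The go/no-go decision depends on a single CR (4 against 5 in 25). If non-CRs can be dropped and replaced, a regimen whose CR rate is 10% among all patients given it gets extra attempts to reach 5. The published CR rate and its interval would also describe patients who completed the opening weeks, not patients given the regimen.

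**Working it through.** **Inputs.** From Sections 10.1 and 10.2.1: p0 = 0.10, p1 = 0.30, n1 = 16, stop at 1 or fewer, n = 25, reject at 4 or fewer. The share d of treated patients who stop before evaluability is not in the documents; it is an assumption, shown from 0 to 20%.

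**Step 1: reproduce the plan.** With X1 ~ Bin(16, p) and X2 ~ Bin(9, p), independent:
- PET = P(X1 ≤ 1). At p = 0.10 this is 0.1853 + 0.3294 = 0.5147 (plan: 0.52).
- Expected sample size = 16 + 9 × (1 − 0.5147) = 20.37 (plan: 20.37).
- Type I error = P(X1 ≥ 2 and X1 + X2 ≥ 5) at p = 0.10. By X1 = 2, 3, 4 and 5 or more, the terms are 0.0145 + 0.0321 + 0.0315 + 0.0170 = 0.0951.
- Power, the same probability at p = 0.30, is 0.9030.

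The design reproduces, and its slack below 0.10 is only 0.0049.

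**Step 2: exclude and replace.** Suppose a share d of treated patients stops early with no CR, is left out, and is replaced. The CR rate among those counted is then p_treated / (1 − d). Putting 0.10 / (1 − d) into the Step 1 formula, and 0.30 / (1 − d) for the bias:

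| d | Counted CR rate, true 10% | Type I error | Counted CR rate, true 30% |
|---|---|---|---|
| 0 | 10.0% | 0.095 | 30.0% |
| 2.4% | 10.2% | 0.103 | 30.7% |
| 4% | 10.4% | 0.109 | 31.3% |
| 5% | 10.5% | 0.112 | 31.6% |
| 10% | 11.1% | 0.133 | 33.3% |
| 20% | 12.5% | 0.190 | 37.5% |

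Type I error crosses 0.10 at d of about 1.5%. At d = 10%, the chance of stopping at stage 1 under the null falls from 0.515 to 0.456. For scale, one early stop in 26 treated patients is 3.8%.

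The 2.4% row is context only. Section 2.3.1 lists pembrolizumab discontinuations for immune events in 2799 patients: 36 + 15 + 6 + 4 + 2 + 1 + 3 = 67, and 67/2799 = 2.4%. These are discontinuations at any time and on pembrolizumab alone.

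**Step 3: compare the rules.** The first three infusions fall at weeks 0, 3 and 6.

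| Patient stops all treatment | Section 10.1 | Section 6.1.9 | Section 5.4.2 |
|---|---|---|---|
| Week 7 | not evaluable | evaluable (three infusions) | replaceable |
| Between weeks 9 and 10 | not evaluable | evaluable | not replaceable |

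The same patient can be in or out of the denominator depending on the section read. A patient in the second row would be excluded without replacement, which the Step 2 model does not cover.

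**The case against.** A reader might infer that type I error does exceed 10%. The documents do not establish this. It requires the 10% null to refer to all treated patients, and Section 10.2.1 speaks only of testing the combination on 16 patients. If the null was meant for patients who received both drugs long enough to be evaluable, type I error is exactly 0.0951. It also requires d above about 1.5%, and no early-stop rate is given.

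A reader might take the 20% toxicity ceiling in Section 10.2.3 as a guide to d. It is a limit on unacceptable toxicity, not a drop-out rate. The discontinuation counts in Section 2.3.1 are closer and much lower. Median onset was 3.3 to 5.1 months for five of the seven event types, later than week 10 (about 2.3 months), so many of those stops would fall after the cut-off. Those counts, however, omit other toxicity, withdrawal, non-compliance and ibrutinib effects, and Section 5.3 itself anticipates drop-out among older and winter-resident patients. They do not bound d either.

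A reader might also assume that every early immune-related stop leaves the analysis. It need not. Section 10.1 asks for only two pembrolizumab cycles, Section 6.1.8 modifies the two drugs separately, and footnote 13 of Section 7.3.7 foresees patients continuing ibrutinib after pembrolizumab. Such a patient can stay evaluable and count as a non-CR.

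Finally, that replacement covers toxicity or progression is inferred from the lack of any exception; it is not stated. Replacement is permitted, not required, and early progression should be uncommon in patients who do not meet treatment criteria. All these points limit the size of the effect. None supplies an all-treated analysis or reverses the direction of the bias.

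**Conclusion.** The point holds in a conditional form. As written, the plan allows treated patients who stop all treatment before about week 10 to be left out of the CR analysis, and those who stop before 9 weeks to be replaced. They are almost certainly non-CRs, so the CR rate is biased upward for the stated objective. At a true 30%, the bias is 1.6 points at d = 5% and 3.3 points at d = 10%.

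Type I error can exceed the stated 10%. On an all-treated null it is 0.109 at d = 4% and 0.133 at d = 10%; on an evaluable-patient null it remains 0.095 and the trial answers a narrower question. These figures assume that every early stopper is a non-CR, is excluded and is replaced, and that d takes the value shown. The conflict between Sections 5.4.2, 6.1.9 and 10.1 needs no assumption. With a cut-off between 4 and 5 CRs, an unsettled denominator could change the decision.

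**What to change.** - Reconcile Sections 5.4.2, 6.1.9 and 10.1 so that there is one evaluability rule and one replacement rule.
- In Sections 10.1 and 10.2.1, define the primary CR set as all patients who receive at least one dose of study drug, count anyone without a documented CR as a non-CR, and apply the Simon counts of 16 and 25 to treated patients.
- In Section 5.4.2, for the primary test, limit replacement to patients who never receive study drug.
- Keep the CR rate in the evaluable set as a labelled supportive analysis.

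This changes wording only. Section 9 already requires dates and reasons for stopping to be recorded, so no procedures or patients are added. Type I error against an all-treated null of 10% is then 0.095 whatever d is.

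The possible cost is power. If the 30% target refers to treated patients, power stays at 0.903. If it was meant for evaluable patients, the treated-patient rate is 0.30 × (1 − d), and power falls to about 0.88 at d = 4%, 0.873 at 5% and 0.837 at 10%. The sponsor should state which population the 10% and 30% describe.

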4 STUDY DESIGN AND ENDPOINTS

4.1 DESCRIPTION OF THE STUDY DESIGN

Trial Design

The trial is an open-label, single arm phase II study to be conducted only at the Moffitt Cancer Center. Anticipated accrual will be 25 subjects. One of the secondary endpoint of this study is reconstitution of immune function, using response to pneumococcal vaccination as a clinical surrogate representation of global immune function. The study is designed to test the null hypothesis that, in high risk CLL (defined as presence of del17p or TP53, del11q or ATM mutation, unmutated IGVH or mutated IGVH with 3.21 phenotype) patients who do not require treatment of CLL and receive PD-1:PD-L1 blockade along with ibrutinib, challenge with the 7-valent pneumococcal vaccine will elicit an immunologic response <40%, defined as the generation of detectable antibody responses to >6 antigens. Our specified alternative hypothesis is that vaccination in the context of PD-1 blockade and ibrutinib will elicit an immunologic response >60% with 90% power.

Overall treatment Schema: All intravenous treatments will be administered at the outpatient Moffitt Cancer Center Infusion Center. The patients will receive a combination of IV pembrolizumab (anti-PD1) and oral ibrutinib according to the scheduled depicted in Figure 1. Briefly, patients will receive pembrolizumab on a 3-week interval schedule for a total of at least 51 weeks (it could be extended for up to 2 years if clinical benefit per investigator); starting with week 6, patients will additionally start daily oral ibrutinib which will be continued through 54 weeks of ibrutinib therapy. The rationale of starting pembrolizumab first is to avoid overlapping toxicity of ibrutinib and the anti-PD1 antibody.

Biomarker Research

Immune Monitoring Laboratory Correlates:

1. Global Immune function will be assessed in terms of serum cytokine patterns. Patient sera will be evaluated by flow cytometric means using cytokine bead arrays to measure serum cytokine levels quantitatively. The cytokine panel will include IFN- γ , TNF- α , IL-2, IL-4, IL-10, IL-6, IL-17A, allowing discrimination between TH1, TH2, and TH17 profiles.

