6.1.9 DURATION OF THERAPY

The duration of ibrutinib therapy will be up to 51 weeks.

The duration of therapy of pembrolizumab will be up to 51 weeks. Pembrolizumab dosing could be extended for up to 2 years if clinical benefit per investigator.

Patients will be considered evaluable if they complete at least 9 weeks or three infusions of pembrolizumab.

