10.2.2 ANALYSIS OF THE SECONDARY ENDPOINT(S)

1. Change in T cell exhaustion and/or inhibition following treatment
2. Change in serum immunoglobulin levels following treatment
3. Progression free survival (PFS) and association with immune biomarkers

To determine if T cell exhaustion or inhibition have change due to treatment with the combination therapy at baseline immune testing to immune testing following completion of pembrolizumab and ibrutinib treatments (week 52) using paired t-tests with the null hypothesis being that there is no change in immune measurements following treatment (i.e., $H_0: \mu_d = 0$). If the assumptions of normality do not hold upon assessment, we will instead use nonparametric t-tests (i.e., Wilcoxon Sign Rank Test). Similar tests will be used to determine if changes in serum immunoglobulin levels also resulted following treatment. Tests will be one-sided as based on biology expect the change in immune response to be in one direction following treatment. Tests will be considered statistically significant if the p-value is less than 0.05. Assuming the study go on to stage II and enroll 25 patients, we will be able to detect a modest effect size of 0.60. To determine the association of progression free survival (PFS) with immune biomarkers (T cell exhaustion and/or inhibition, serum immunoglobulin levels), Cox proportional hazards models will be fit with assumption of proportional hazards (PH) assumption check via Schoenfeld residuals. If the PH assumption does not hold, we will rely on use of non-parametric methods (Kaplan-Meier curve with log-rank tests) where the biomarkers will be dichotomized for analysis based on an optimal cut-point determination based on an outcome-oriented approach outlined by Contral and O'Quigley (Contal C, O'Quigley J. An application of changepoint methods in studying the effect of age on survival in breast cancer. Computational Statistics & Data Analysis. 1999;30:253-70.). A Cox regression of the log hazard ratio on the continuous biomarker (assuming a standard deviation of 1 and an anticipated event rate of 0.50) will have 80% power at a 0.05 significance level to detect a regression coefficient equal to 0.79 (i.e., hazard ratio of 2.20).

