10.2.4 EXPLORATORY ANALYSES

Biological samples for each of the 25 patients enrolled in the trial will be collected at 4 time-points. As the correlative experiments are not the primary focus of the study and are more exploratory in nature, no sample size / power calculations were completed. Summary statistics will be used to summarize the quantitative measures (e.g., cytokine levels, expression levels) for the patients at the 4 time-points with two-sample t-test use to determine if quantitative measurements differ between patients that response and patients that do not response at each time point. When assessing changes in quantitative measurements between time-points (e.g., pre and post treatment measurements) paired t-tests will be used. Longitudinal analysis with linear mixed models will also be used to look for statistical differences between the responders and non-responders using quantitative measurements at all 4 time-points. Correlation between quantitative measurements will be assessed with Spearman correlation.

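### Section 10.1 uses one evaluable set, reached at about week 10, for both efficacy and safety; no all-treated set exists, three sections disagree on who is evaluable or replaceable, and the Simon counts of 16 and 25 name no set

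*Combined protocol and SAP*

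**What the plan says.** Section 10.1 defines patients evaluable for response as those "receiving at least 4 weeks into ibrutinib therapy and at least 2 cycles of pembrolizumab. It will be used for efficacy and safety analysis". Section 4.1 says that "starting with week 6, patients will additionally start daily oral ibrutinib". No intention-to-treat, all-treated or safety population is defined anywhere.

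Two other sections bear on the same patients:

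- Section 6.1.9: "Patients will be considered evaluable if they complete at least 9 weeks or three infusions of pembrolizumab".
- Section 5.4.2, whose replacement rule covers screen failures as well, says of early leavers: "drop out prior to completing 9 weeks of treatment are permitted to be replaced in order to meet the accrual goal of this study".

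The decision rule in Section 10.2.1 reads "After testing the drug combination on 16 patients in the first stage, the trial will be terminated if 1 or fewer respond", and the combination is rejected if 4 or fewer of a total of 25 respond. It does not say which patients are counted. Elsewhere the 25 is accrual (Section 4.1: "Anticipated accrual will be 25 subjects") or enrolment (Section 10.2.2: "Assuming the study go on to stage II and enroll 25 patients"; Section 10.2.4: "Biological samples for each of the 25 patients enrolled in the trial will be collected at 4 time-points"). Section 10.2.3 applies its toxicity boundary to the first 16 patients and then reviews all 25, without saying whether these are treated or evaluable.

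**The concern.** A set that requires about ten weeks on study can be defended for a response analysis. It is the wrong set for safety, because it removes the patients most likely to have stopped for toxicity. The protocol's own figures put much of the expected toxicity inside the excluded window. Section 2.3.1 gives median onset times for pembrolizumab of 1.3 months for hepatitis, 1.4 for hyperthyroidism and 1.2 for thyroiditis, whereas week 10 is about 2.3 months. Under Section 6.1.8 a Grade 3 or 4 infusion reaction ends trial treatment permanently, so a patient who has one at the first infusion can never enter the only set named for safety.

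For efficacy, early leavers may still be followed for disease status (Section 5.4.1), and one drug can be stopped alone. They are nevertheless unlikely to be recorded as CR before the first scheduled response assessment at week 12 (Section 7.1.15), so leaving them out tends to raise the CR rate. With no named set and three competing rules, two readers could apply the stage 1 stop and the final rule to different patients.

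**Working it through.** **The three rules side by side.** Earliest evaluability under Section 10.1 is week 6 + 4 weeks = week 10. Pembrolizumab is given at weeks 0, 3 and 6, so the third infusion falls at week 6.

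| Patient stops treatment | Section 6.1.9 | Section 10.1 | Section 5.4.2 |
|---|---|---|---|
| Week 7, if three infusions is met on the day of the week 6 infusion | evaluable | not evaluable | replaceable |
| Between weeks 9 and 10 | evaluable | not evaluable | not replaceable |

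**The plan's own figures.** Exact two-stage binomial: continue if more than 1 of 16 respond, declare active if more than 4 of 25 respond.

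- At p = 0.10: P(X ≤ 1 of 16) = 0.515; expected size 16 + 9 × (1 − 0.515) = 20.37; type I error 0.0951.
- At p = 0.30: power 0.9030.

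This reproduces the stated design; the printed early-termination probability of 0.52 against 0.515 is only rounding. For the boundary in Section 10.2.3 (3 at n = 3; 4 at 4–6; 5 at 7–9; 6 at 10–12; 7 at 13–16), the exact probability of crossing by n = 16 at a 20% rate is 0.0496, against the stated 0.05. The arithmetic of both rules is sound. What is missing is who is counted.

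The documents give no early exit rates, so all those below are assumptions.

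**1. Toxicity boundary.** Let q be the true rate of dose-limiting toxicity (DLT) and f the fraction of DLT patients who leave before week 10 and are replaced. If n counts only Section 10.1 patients, the observed rate is q(1 − f)/(1 − qf). At q = 0.40:

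| f | Observed rate | P(halt by n = 16) |
|---|---|---|
| 0 (all treated counted) | 0.400 | 0.529 |
| 0.25 | 0.30/0.90 = 0.333 | 0.321 |
| 0.50 | 0.20/0.80 = 0.250 | 0.119 |

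**2. Simon type I error, if the 10% null refers to all treated patients and leavers are replaced.** With exit fraction d and CR rate c among leavers, the evaluable CR rate under the null is (0.10 − c·d)/(1 − d).

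| d | c = 0: rate, type I error | c = 0.05: rate, type I error |
|---|---|---|
| 5% | 0.1053, 0.112 | 0.1026, 0.104 |
| 10% | 0.1111, 0.133 | 0.1056, 0.113 |
| 15% | 0.1176, 0.159 | 0.1088, 0.125 |
| 20% | 0.1250, 0.190 | 0.1125, 0.139 |

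With no exits, or if the null refers to evaluable patients, it stays at 0.095.

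**3. Power, if 25 are enrolled and some stage 2 patients are neither evaluable nor replaceable.** With the same boundaries, 16 + 8 = 24 patients give power 0.884 (type I error 0.083), and 16 + 7 = 23 give 0.861 (0.072), against the stated 0.90.

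**The case against.** The best reply is that Section 10.1 sets out who is evaluable for response, states the 30% CR hypothesis, and is followed directly by the test of that hypothesis. The 16 and 25 are then naturally read as evaluable patients, and type I error stays at 0.095. Section 5.4.2 allows replacement to reach the accrual goal, so accrual of 25 may already be net of early drop-outs. Three 3-weekly infusions make nine weeks of treatment, so 6.1.9 and 5.4.2 can be read as one threshold, which leaves a gap of about a week to the 10.1 rule. On safety, adverse events are collected from consent (Section 8.3). Section 10.2.3 monitors continuously without mentioning evaluability, and the Protocol Monitoring Committee sees serious events as they are reported. The toxicity illustration also stacks a 40% true rate on early exit and replacement, while replacement is only permitted, and only before 9 weeks.

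Much of this limits the size. The evaluable reading of the Simon counts is reasonable, the week 7 case depends on how three infusions is counted, and the loss to 24 or 23 patients would ordinarily need exits in a narrow window. The toxicity figures are conditional and do not forecast what will happen. None of it supplies a safety set, and the week 9 to 10 conflict remains on any reading. Complete collection of adverse events does not help if the analysis set written for them excludes the patient.

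**Conclusion.** The concern holds and should be fixed before analysis. Two parts need no assumption: the only set named for safety excludes anyone who stops before about week 10, and Sections 10.1, 6.1.9 and 5.4.2 classify some patients in incompatible ways. The Simon counts and the toxicity n are not tied to a named set.

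The numerical consequences are conditional. The fall in halting probability needs the boundary to count Section 10.1 patients, with early DLT leavers replaced. The rise in type I error needs the null to refer to all treated patients. The power loss needs enrolled patients who are neither evaluable nor replaceable. If the null refers to evaluable patients and all 25 are evaluable, the Simon design keeps its stated error rates.

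**What to change.** 1. In Section 10.1, define the safety set as all patients who received any dose of either drug. In Section 10.2.3, state that n counts these patients in order of first dose.
2. Reconcile Sections 10.1, 6.1.9 and 5.4.2 to one evaluability and replacement definition. State in Section 10.2.1 that the 16 and 25 count that named set, and align the accrual and enrolment wording in Sections 4.1, 10.2.2 and 10.2.4 with it.
3. Alongside the evaluable-set result, report the CR rate with its exact 95% CI in all treated patients, counting a missing CR assessment as non-CR. List every excluded or replaced patient with the reason.

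The cost is wording in these sections and one extra table. Adverse events and the dates and reasons for stopping are already recorded (Sections 8.3 and 9). The all-treated CR rate will look slightly lower: for example, 5/25 = 20.0% (95% CI 6.8 to 40.7) against 5/28 = 17.9% (6.1 to 36.9) if three patients were replaced.

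If the sponsor prefers all treated patients as the primary set, the power in Section 10.2.1 must be restated. Suppose the 30% was meant for evaluable patients and leavers count as non-CR, so that p = 0.30(1 − d). Power then falls below 0.90 once exit exceeds about 0.6%, and is 0.873, 0.837, 0.793 or 0.742 at 5, 10, 15 or 20% exit.
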